**Relypsa For ED Acute Hyperkalemia Control and Reduction
(REDUCE)**

NCT 02933450

June 21st 2017

Protocol and Statistical Analysis

Study design and setting: This is a single center, single blinded, open label, feasibility pilot study performed at a large inner-city academic ED. The study was approved by the institutional review board.

Selection of participants: Patients ≥ 18 years of age and ESRD, who had serum potassium ≥ 6.0 mEq/L, were eligible for enrollment. Exclusions were: i) a significant arrhythmia on initial EKG (determined by clinical provider), ii) known allergy to patiromer, iii) an oral potassium binder administered prior to enrollment, iv) pregnancy, v) not anticipated to need medical management of hyperkalemia for at least 4 hours (i.e. hemodialysis unit and staff available for emergent dialysis and medical management is not necessary).

Interventions: After obtaining informed consent, patients were randomly assigned to standard-of-care (SOC) or a single dose of 25.2g oral patiromer plus SOC (PAT) cohort. Standard-of-care is defined as intervention provided by clinical provider according to individual practice pattern or hospital protocol. Providers were blinded to treatment assignment and all data gathered by the research team. Patients were observed with telemetry monitoring for up to 10 hours or until they received hemodialysis, whichever occurred first. Blood draws and electrocardiograms (ECGs) were performed at enrollment and at 1, 2, 4, 6 and 8hrs hours thereafter.

Outcomes: The primary outcome was the difference in serum potassium between SOC and PAT groups at 2, 4, and 6 hours. Recorded adverse events included rates of new gastrointestinal symptoms, hypomagnesemia, and hypoglycemia.

Analysis: Demographic characteristics were analyzed with Wilcoxon rank sum and Chi-squared test. Baseline serum potassium was compared using median and inter-quartile range (IQR). A mixed-effect linear regression model with an unstructured covariance structure was used to model potassium levels by adjusting for time, group interaction, and baseline potassium. The adjusted means of potassium levels over time were computed for each group. Contrasts between the two groups at each time point were evaluated and adjustment of multiple comparisons was made using Bonferroni's method. The amount of insulin and albuterol given and the number of interventions within 2, 4, and 6 hours were compared using the Wilcoxon rank sum test.

Adverse events were reported and analyzed using Fischer's exact test or Chi squared test. Analyses were conducted per protocol basis; patients who went for hemodialysis treatment before 4hrs of medical treatment were excluded from the analysis

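### Adverse events are compared as crude proportions although observation may run from about 4 h to 10 h, so a between-arm difference in time to dialysis could show or hide a difference in harm

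*Combined protocol and SAP*

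**What the plan says.** All of this is in the combined protocol and SAP, under unnumbered headings.

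- **Observation (Interventions):** "Patients were observed with telemetry monitoring for up to 10 hours or until they received hemodialysis, whichever occurred first". This is the only observation period in the document.
- **Assessments (Interventions):** "Blood draws and electrocardiograms (ECGs) were performed at enrollment and at 1, 2, 4, 6 and 8hrs hours thereafter".
- **Harms (Outcomes):** "Recorded adverse events included rates of new gastrointestinal symptoms, hypomagnesemia, and hypoglycemia". No time window or denominator is attached.
- **Test (Analysis):** "Adverse events were reported and analyzed using Fischer's exact test or Chi squared test".
- **Analysis set (Analysis):** "patients who went for hemodialysis treatment before 4hrs of medical treatment were excluded from the analysis".
- **Blinding (Interventions):** "Providers were blinded to treatment assignment and all data gathered by the research team".

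By contrast, the Analysis section compares insulin, albuterol and the number of interventions over fixed windows of 2, 4 and 6 hours. It states no such window for adverse events. It also does not plan to report observation time or time to dialysis by arm.

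**The concern.** Fisher's exact and chi-squared tests compare the proportion of patients with an event and take every patient as equally observed. If observation stops at dialysis, that is not so here. An analysed patient dialysed at 4.5 h has draws at 1, 2 and 4 h. One not dialysed has draws at 1, 2, 4, 6 and 8 h and up to 10 h of observation. The second patient has more chances to show hypomagnesemia, hypoglycemia or a new gastrointestinal symptom.

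Within one arm this only blurs what the proportion means. It matters for the comparison if time to dialysis differs between arms. That could happen because the study drug is given to lower potassium, and potassium may bear on the urgency of dialysis. It could also happen by chance. The arm observed longer then collects more counted events with no true excess, or a true excess in the arm observed for less time is diluted.

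This concerns time at risk among the patients who are analysed. Which patients belong in the safety set is a separate matter.

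**Working it through.** The documents give no adverse-event rate, dialysis-time distribution or arm size, so there is no figure of the plan's own to reproduce. What follows is illustration.

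**Inputs from the documents:** a maximum of 10 h; a minimum of about 4 h for analysed patients; post-baseline draws at 1, 2, 4, 6 and 8 h. **Assumed:** a constant event hazard h per hour (0.02, 0.05 or 0.10); every patient in an arm followed for that arm's mean time; 15 or 30 patients per arm for the test calculations.

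**1. Bounds.** The largest possible ratio of time at risk is 10/4 = 2.5. For laboratory events the last scheduled draws fall at 4 h and 8 h, a ratio of 8/4 = 2. The exclusion counts 4 h of medical treatment while the draws count from enrollment, so the lower bound is approximate.

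**2. Apparent harm with no true difference.** Crude risk = 1 - exp(-h × t), with the same h in both arms.

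| h per hour | 6 h v 8 h | ratio | 4 h v 10 h (extreme) | ratio |
|---|---|---|---|---|
| 0.02 | 11.3% v 14.8% | 1.31 | 7.7% v 18.1% | 2.36 |
| 0.05 | 25.9% v 33.0% | 1.27 | 18.1% v 39.3% | 2.17 |
| 0.10 | 45.1% v 55.1% | 1.22 | 33.0% v 63.2% | 1.92 |

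For example, at 0.05: 1 - exp(-0.30) = 25.9% and 1 - exp(-0.40) = 33.0%. With equal follow-up the ratio is 1.0.

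**3. Hidden harm.** In this model crude risks are equal when the hazard ratio (patiromer to SOC) equals SOC time divided by patiromer time: 8/6 = 1.33, or 10/4 = 2.5 at the bounds. With a true hazard ratio of 1.5, SOC hazard 0.05, SOC followed for 8 h and patiromer for 6 h, the risks are 33.0% and 1 - exp(-0.45) = 36.2%. With 8 h in both arms they would be 33.0% and 1 - exp(-0.60) = 45.1%.

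**4. Effect on the tests.** Probability of a two-sided p < 0.05 at h = 0.05 in both arms, by exact binomial enumeration (chi-squared uncorrected):

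| Follow-up | Fisher, n = 15 / 30 per arm | Chi-squared, n = 15 / 30 per arm |
|---|---|---|
| 6 h v 6 h | 1.8% / 2.6% | 5.5% / 4.9% |
| 6 h v 8 h | 2.7% / 5.4% | 7.6% / 9.0% |
| 4 h v 10 h | 13% / 34% | 26% / 45% |

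For modest differences in follow-up and small arms, the main effect is on the estimate rather than on false significance.

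**5. Which remedies equalise time at risk.**

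- *Fixed 0-4 h window.* Under equal hazards both arms have the same risk: 7.7%, 18.1% or 33.0% at the three hazards.
- *Cumulative incidence with dialysis as a competing event.* If dialysis and 10 h are the only ends of observation, nothing else is censored and the 10 h cumulative incidence is the crude proportion. Take an event hazard of 0.05 and a dialysis hazard d after 4 h. The incidence is [1 - exp(-0.20)] + exp(-0.20) × 0.05/(0.05 + d) × [1 - exp(-6(0.05 + d))]. For d = 0.05 this is 0.181 + 0.185 = 36.6%. For d = 0.20 it is 0.181 + 0.127 = 30.8%. The ratio of 1.19 remains.
- *Events per patient-hour.* This corrects only if the hazard is roughly constant. Suppose 20% in each arm have an event, all before 4 h. The proportions agree, but the rates at 6 h and 8 h are about 0.20/6 = 0.033 and 0.20/8 = 0.025 per hour, a false ratio of 0.75 favouring the arm followed longer.

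**The case against.** The strongest reply is that much of this is inference. The sentence that ends observation at dialysis is about telemetry, and nothing says that recording of gastrointestinal symptoms stopped then. No dialysis trigger is given. The nearest text is the exclusion of patients "not anticipated to need medical management of hyperkalemia for at least 4 hours", which turns on the availability of the dialysis unit and staff. Providers knew neither the assignment nor the research data. The follow-up times of 6 h and 8 h are chosen, not sourced. Even the fourfold difference in dialysis hazard used above gives mean follow-up of 9.2 h against 7.5 h and a ratio of only 1.19. A continuous hazard is also a rough description of laboratory events seen only at scheduled draws, with none after 8 h. Finally, events before dialysis or 10 h is a legitimate quantity in patients with ESRD, and harms are not the primary outcome of this feasibility pilot.

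Most of this stands, and it limits the claim. A reader might infer that adverse-event recording is known to have stopped at dialysis, that patiromer is known to defer dialysis, or that the harm comparison is therefore biased against it. The documents establish none of these.

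It does not remove the point. No other adverse-event window is offered. Blinding narrows the route from treatment to dialysis timing but does not close one that acts through potassium or symptoms, and it does nothing about chance imbalance. The legitimate quantity still needs observation time beside it if a difference between arms is to be read as a difference in harm.

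**Conclusion.** The point holds as a statement of what can happen, not of what did. On the only observation period stated, analysed patients may have about 4 h to 10 h at risk and three to five post-baseline draws, and the planned tests ignore this. At an assumed hazard of 0.05 per hour, 6 h against 8 h produces an apparent risk ratio of 1.27 with no true difference. At the document's own bounds, which are an extreme case, the ratio is 1.92 to 2.36 over the hazards tried. If follow-up is equal between arms there is no distortion. The actual size cannot be worked out from the documents.

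Two stronger conclusions are tempting and should be resisted. One is that the harm comparison cannot be read at all: the 4 h exclusion gives every analysed patient about 4 h of follow-up and caps the ratio near 2.5, although as a post-randomisation exclusion it does not make follow-up alike. The other is that the tests will be falsely significant: at 6 h against 8 h, Fisher's test stays near or below 5% for the arm sizes assumed.

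**What to change.** 1. State the adverse-event window, and whether recording continued after dialysis began.
2. Add a between-arm comparison over a fixed window from enrollment to 4 h, by Fisher's exact test. Use the 1, 2 and 4 h draws for laboratory events, and gastrointestinal symptoms with onset by 4 h where onset time was recorded.
3. Keep the full-period proportions, labelled as events before dialysis or 10 h. Put median observation time and time to dialysis by arm beside them.
4. Show events per patient-hour, if at all, only as a supplement that states its assumption of a roughly constant hazard. Cumulative incidence with dialysis as a competing event should not be offered as a correction, because here it returns the crude proportion.

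The cost is some analysis wording and a few table rows. It needs the actual time of dialysis, not only whether it came before 4 h, and symptom onset times, which the documents do not say were collected. The 0-4 h comparison omits later events, but the full-period table still shows them.

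### Magnesium is analysed only as a hypomagnesemia rate; adding a baseline-adjusted analysis of the measured values would be a cheap, optional gain in sensitivity at pilot size

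*Combined protocol and SAP*

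**What the plan says.** All sections of the combined protocol and SAP are unnumbered.

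- **Outcomes.** Magnesium appears once: "Recorded adverse events included rates of new gastrointestinal symptoms, hypomagnesemia, and hypoglycemia". No cut-off, grading or time window is given for hypomagnesemia.
- **Analysis, adverse events.** "Adverse events were reported and analyzed using Fischer's exact test or Chi squared test". No rule says which test applies when.
- **Analysis, potassium.** "A mixed-effect linear regression model with an unstructured covariance structure was used to model potassium levels", with terms for time, the group interaction and the baseline value. On multiplicity: "Contrasts between the two groups at each time point were evaluated and adjustment of multiple comparisons was made using Bonferroni's method". Neither sentence extends to magnesium.
- **Interventions.** "Blood draws and electrocardiograms (ECGs) were performed at enrollment and at 1, 2, 4, 6 and 8hrs hours thereafter". The section does not say which assays were run at which draw.
- **Study design and setting.** The trial is a "single center, single blinded, open label, feasibility pilot study". No sample size, alpha or power is stated.

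**The concern.** Hypomagnesemia is a threshold on a continuous laboratory value. Classifying a patient requires a magnesium measurement, yet the plan uses only which side of the threshold the value fell on. The size of the change is lost, and no adjustment for the enrollment value is planned.

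A feasibility pilot is poorly suited to comparing uncommon events between arms, but it can estimate a mean shift with a confidence interval. At stake is what the pilot tells a later trial about magnesium. A non-significant comparison of a few cases carries little information, whereas an estimated difference with its interval shows which shifts remain compatible with the data. The potassium analysis already contains the type of model needed.

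**Working it through.** **1. Nothing to reproduce.** The plan states no power or sample size for this outcome, so what follows is a comparison of methods under assumptions.

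**2. Assumed inputs.** Analysed patients per arm n = 15, 20 or 30, allocated 1:1, after the exclusion of patients dialysed before 4 hours; two-sided alpha 0.05; Normal magnesium with equal SD; one post-dose time; correlation with the enrollment value r = 0.5; standard-of-care (SOC) rate p0 = 5%.

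**3. Linking shift and rate.** A lowering of d SD moves the share below the threshold from p0 to p1 = Φ(Φ⁻¹(p0) + d). For 5% to 20%, d = −0.842 − (−1.645) = 0.803. For 5% to 30%, d = −0.524 + 1.645 = 1.12.

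**4. Power.**
- Binary: sum the binomial probabilities of all outcome pairs for which Fisher's test, or the uncorrected chi-squared test, gives p ≤ 0.05.
- Measured value: noncentral t with noncentrality d/√(1 − r²) × √(n/2) and 2n − 3 degrees of freedom. For d = 0.803 and n = 20: 0.803/0.866 = 0.927, times √10 = 3.162, gives 2.93. The critical value is 2.03 and the power 81.5%.
- Because the potassium contrasts carry Bonferroni, the measured value is also shown at 0.05/3 = 0.0167, for the three primary time points.

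Power in %, at 15 / 20 / 30 per arm:

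| Shift (SOC 5% to) | Fisher | Chi-squared | Measured, 0.05 | Measured, 0.05/3 |
|---|---|---|---|---|
| 0.25 SD (8.2%) | 0.3 / 0.8 / 0.8 | 1.5 / 3.1 / 6.5 | 11.9 / 14.4 / 19.6 | 5.1 / 6.5 / 9.6 |
| 0.50 SD (12.6%) | 1.5 / 3.9 / 4.9 | 5.5 / 10.0 / 18.1 | 33.2 / 42.8 / 59.4 | 18.5 / 26.2 / 41.5 |
| 0.80 SD (20%) | 8.3 / 16.8 / 24.1 | 18.8 / 29.2 / 45.3 | 68.8 / 81.5 / 94.2 | 50.5 / 66.5 / 86.6 |
| 1.12 SD (30%) | 27.5 / 44.6 / 63.1 | 44.6 / 59.1 / 77.8 | 92.7 / 97.8 / 99.8 | 83.1 / 93.8 / 99.4 |

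**5. Wider grid.** Take 36 scenarios: 10, 15, 20 or 30 per arm; SOC rate 1%, 5% or 10%; shift 0.5, 0.8 or 1.0 SD; r = 0.5. Fisher's power is below 20% in 28. The measured value at 0.05 has at least twice Fisher's power in 35 and at least twice chi-squared's in 30. At 0.05/3 it has at least twice chi-squared's power in only 21, but it is never lower (smallest ratio 1.27).

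**6. Serial case.** A simulation (3,000 runs per cell) compared Fisher's test on any low value at 2, 4 or 6 hours with three Bonferroni-adjusted contrasts. With 15 per arm, 5% low per draw, r = 0.5 and an effect rising to 1 SD at 6 hours, power was 20% against 77%. With 0.5 SD it was 4% against 23%.

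**7. A check that needs no assumed effect.** With no SOC cases, Fisher's test first reaches p < 0.05 at 5 patiromer cases with 10, 15 or 20 per arm (p = 0.033, 0.042, 0.047) and at 6 cases with 30 per arm (p = 0.024). Four cases against none is non-significant at each of these sizes (p = 0.087 to 0.112).

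**The case against.** The strongest reply is that this is a conventional adverse-event analysis in a feasibility pilot. Counts are what clinicians read, a mean shift is not a clinical event, and nothing in the documents says a non-significant test will be taken as evidence of safety. That stands. It makes the change optional and means the counts must be kept.

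The size of the gain is also open to challenge. Every input is assumed, and nothing in the documents supports a shift as large as 0.8 SD after a single dose with at most 10 hours of observation. The plan allows chi-squared as well as Fisher, and copying the potassium model brings Bonferroni with it. Each of these narrows the gap. In the 5% v 20% case it falls from about 4 to 8 times (Fisher against the measured value at 0.05) to about 2 to 3 times (chi-squared against 0.05/3). At 0.05/5, for all five post-enrollment draws, the measured value has 42%, 59% and 82%, still above chi-squared. The calculation also ignores departures for dialysis and the cost of estimating an unstructured covariance in a small sample.

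Four stronger readings are tempting, and the documents do not support them:

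- *The binary comparison has almost no power.* This holds for uncommon events and small or moderate shifts. It fails for 5% v 30% at 30 per arm, where Fisher has 63%.
- *Patients already low at enrollment are counted as events.* Hypomagnesemia is not defined, and the word "new" in the Outcomes list may govern all three items.
- *Serial magnesium values exist.* The schedule lists blood draws, not magnesium assays.
- *Glucose should be modelled the same way.* No calculation here covers it, and insulin is given at provider discretion, so a mean glucose difference could reflect co-treatment.

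**Conclusion.** The point holds in a limited form. The plan reduces magnesium to a rate and compares proportions, and no analysis of the measured values is specified. At pilot size, with uncommon hypomagnesemia and a moderate shift, that comparison has low power, and a baseline-adjusted analysis of the same measurements is more sensitive. The direction survived the choice of binary test and the Bonferroni penalty at 0.05/3 throughout the 36-scenario grid.

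The size cannot be fixed from the documents. It rests on assumed n, alpha, rates, Normality, equal SD and r = 0.5. If the true shift is about 0.25 SD, neither analysis would show it reliably; the measured value would still give an interval on the difference. This is an optional, cheap improvement to a secondary safety analysis. It does not touch the primary outcome and is not an error that invalidates the plan.

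**What to change.** Add to the Analysis section, for example:

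> Serum magnesium is analysed as a measured value, adjusted for the enrollment value. If it was assayed at several post-dose draws, a mixed model of the type used for potassium is fitted; if at one post-dose draw, ANCOVA. The between-arm difference is reported with a 95% confidence interval at each draw where magnesium was measured. Counts of hypomagnesemia by arm are reported descriptively with exact confidence intervals.

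The same section should state the draws at which magnesium was assayed and the cut-off that defines hypomagnesemia, since both the model and the counts depend on them.

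The cost is one further run of a model type already specified, on values needed anyway to classify hypomagnesemia. It adds no visits or samples if an enrollment magnesium value exists; without one, the comparison would have to be unadjusted. The downside is that a mean difference could be read as a clinical event, or could mask a few very low individual values, so the counts must stay beside it.

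### Holm in place of Bonferroni, on whichever set of time-point contrasts is intended, is a cheap improvement: same 5% familywise ceiling and a modest gain in power per contrast

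*Combined protocol and SAP*

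**What the plan says.** The Outcomes section defines the primary outcome at three times: "The primary outcome was the difference in serum potassium between SOC and PAT groups at 2, 4, and 6 hours". Under Interventions, blood draws and ECGs "were performed at enrollment and at 1, 2, 4, 6 and 8hrs hours thereafter", which makes five post-enrollment times. The Analysis section fits a mixed model to potassium and then states: "Contrasts between the two groups at each time point were evaluated and adjustment of multiple comparisons was made using Bonferroni". It does not give the number of contrasts in the family, the familywise level or the sidedness.

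Three contrasts is the better reading. It matches the primary outcome, and the next Analysis sentence uses the same times for rescue-type interventions: "the number of interventions within 2, 4, and 6 hours were compared using the Wilcoxon rank sum test". Five is possible, because the contrast sentence covers every time point without restriction.

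Two further statements bear on the size of the point. The trial is a "single center, single blinded, open label, feasibility pilot study", with no stated sample size or power target. Follow-up runs "for up to 10 hours or until they received hemodialysis, whichever occurred first", and "patients who went for hemodialysis treatment before 4hrs of medical treatment were excluded from the analysis". A patient dialysed between 4 and 6 h therefore stays in the analysis but may have no 6 h value.

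**The concern.** Bonferroni holds every contrast to the strictest threshold, even after another contrast in the family has already been rejected. Holm relaxes the threshold for the second and later contrasts and keeps the same familywise bound. Because the primary outcome names three times, the second and third contrasts matter, and that is where Bonferroni gives up power. What is at stake is some power to show a difference at more than one time. The validity of the result is not in question, nor is the chance of finding any difference at all.

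**Working it through.** **Inputs from the documents.** Three primary contrasts (2, 4, 6 h; Outcomes), five post-enrollment draws (Interventions) and Bonferroni adjustment (Analysis). There is no power, alpha or sample-size figure to reproduce.

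**Assumptions, none in the documents.** Familywise level 0.05 two-sided; contrasts normal with expected value z = difference/SE; correlations between contrasts 0 to 0.9.

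**Thresholds.**
- Bonferroni over three: 0.05/3 = 0.0167, so |z| > 2.394 for every contrast.
- Holm over three, from the largest |z| down, stopping at the first failure: 0.05/3, 0.05/2 and 0.05, so 2.394, 2.241 and 1.960.
- Bonferroni over five: 0.05/5 = 0.01, so 2.576.

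Holm's first step is Bonferroni's threshold. Two results follow without simulation: Holm rejects whatever Bonferroni rejects, and the chance of at least one rejection is identical.

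**Power per contrast.** Under Bonferroni, power is Φ(z − threshold). At z 2.5 this is Φ(2.5 − 2.394) = Φ(0.106) = 54.2% over three and Φ(2.5 − 2.576) = Φ(−0.076) = 47.0% over five. Holm was simulated with up to 1,000,000 draws per case. Ranges are over the correlations.

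| Expected z at the three times | Contrast | Bonferroni % | Holm % | Gain, points |
|---|---|---|---|---|
| 0 / 0 / 2.5 | affected time | 54.2–54.3 | 54.2–54.5 | 0–0.2 |
| 0 / 2.5 / 2.5 | each affected time | 54.2 | 56.9–57.7 | 2.7–3.4 |
| 0.5 / 1.5 / 2.5 | strongest | 54.2 | 54.2–55.6 | 0–1.4 |
| 0.5 / 1.5 / 2.5 | middle | 18.5 | 21.2–22.8 | 2.7–4.3 |
| 2.5 / 2.5 / 2.5 | each | 54.2 | 60.2–62.7 | about 6–8.5 |
| 5 / 5 / 2.2 | weakest | 42.3 | 59.5 | about 17 |

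The ceiling on the gain is Φ(z − 1.960) − Φ(z − 2.394). It is largest at z = 2.18: Φ(0.22) − Φ(−0.214) = 17.2 points. Over a grid of 325 contrast-scenarios with a true effect, the median gain was 3.2 points, and 88% gained 8 points or less.

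**If five contrasts were meant.** With equal z 2.5 at all five times, Bonferroni gives 47% per contrast and Holm over five gives about 55–56%.

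**Thinner 6 h data.** Suppose 80% to 50% of patients have a 6 h value (assumed). Then z at 6 h falls from 2.5 to 2.5 × √0.8 = 2.236, or 2.5 × √0.5 = 1.768. With the same per-patient effect at all times, the gain is 2.9–7.5 points at 2 and 4 h and 7.9–13.7 at 6 h. With no effect at 2 h, it is 0.2–2.8 at 4 h and 3.1–4.8 at 6 h.

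**Small samples.** With t-tests at each time, 10 to 30 per arm (assumed) and equal z 2.5, power is 46–52% with Bonferroni and 53–60.5% with Holm. This is a rough check, because it does not fit the planned mixed model.

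**Realized familywise error.** When no contrast has an effect, the two methods agree (about 4% each at correlation 0.7). When some do, they differ: at z 0/2.5/2.5, about 1.7% with Bonferroni and 3.3% with Holm; at z 0/4/4, 1.7% and 3.7–4.8%. Both stay within 5%.

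**Disagreement with Bonferroni intervals.** At least one contrast is rejected by Holm while its Bonferroni-over-three interval includes zero in about 1% of trials (effect at one time), 7–8% (two times) or 14–23% (three equal effects).

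**The case against.** The strongest case against is that nothing needs correcting. Bonferroni is valid, the trial is a feasibility pilot, and the plan sets no power target. All of that stands and limits the point to minor. A reader might go further and infer that choosing Bonferroni is an error. The documents do not support that, because either method controls the familywise error.

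A reader might also infer that Holm leaves the error rate unchanged. Only the 5% ceiling is shared. In the two-time scenario realized error roughly doubles, for about 3 points of power per true contrast.

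The gain and the reporting cost are also the same event: every rejection that Holm adds is a contrast whose Bonferroni interval includes zero. For a pilot mainly concerned with estimation, preferring a method with matching intervals is defensible. The plan mentions no intervals, however, so this cost is only potential.

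A third tempting inference is that 1 h and 8 h must become descriptive. Holm does not require that. If all five contrasts were meant, narrowing to three is a separate change that takes those two times out of the tested family, each of which has 47% power at z 2.5 under Bonferroni over five. Moving from Bonferroni over five to Holm over three shows gains of 0.3 to 24.2 points, but part of that comes from the smaller family.

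Finally, the text is in the past tense. If the analysis is complete, switching method would be post hoc.

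**Conclusion.** The point holds as a cheap improvement of minor weight. That Holm dominates Bonferroni on the same family at the same ceiling is a mathematical fact and needs none of the assumptions above. The size of the gain does depend on them. For the three primary times it is negligible if only one time shows an effect, about 3 points per contrast with two and 6 to 8 with equal effects at all three, which is a favourable case. Larger gains, up to about 17 points, need a weak contrast beside strong ones. Since the documents fix neither the effect pattern nor the sample size, no single figure can be assigned to this trial. The unstated family size should be settled whichever method is kept.

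**What to change.** In the Analysis section, name the family of contrasts, the familywise level and its sidedness, and replace Bonferroni with Holm on that family.

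- If the family is the 2, 4 and 6 h contrasts, which fits the stated primary outcome, apply Holm over three. Keep 1 h and 8 h in the model and report those contrasts as descriptive.
- If all five contrasts were meant, apply Holm over five and keep them all.
- State that the Holm-adjusted p-value decides each contrast. Label any Bonferroni intervals as such, and note that they can include zero for a contrast that Holm rejects.
- If the analysis is already done, state the divisor that was used and label any Holm results post hoc.

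This takes one or two sentences and a standard software option, with no extra patients or data. The statistical costs are a higher realized familywise error (still at or below 5%) when some contrasts are null, and the lack of simple simultaneous intervals that match the Holm decisions.

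### Adverse events are compared only by a significance test, with no risk difference or interval, so a non-significant result would not show how much excess harm is still possible

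*Combined protocol and SAP*

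**What the plan says.** The Outcomes paragraph lists the safety endpoints: "Recorded adverse events included rates of new gastrointestinal symptoms, hypomagnesemia, and hypoglycemia". The closing text of the Analysis paragraph gives their whole analysis: "Adverse events were reported and analyzed using Fischer's exact test or Chi squared test". Neither place states a risk difference, ratio, confidence interval, upper limit or margin for these events. No significance level is given, and the Bonferroni adjustment is stated only for the potassium contrasts.

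The Study design paragraph describes a "feasibility pilot study performed at a large inner-city academic ED". The document gives no sample size, and the text on interventions gives no allocation ratio. The analysis is per protocol, and "patients who went for hemodialysis treatment before 4hrs of medical treatment were excluded from the analysis". That lowers the number analysed by an amount that is not stated.

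The potassium analysis, by contrast, is set out partly as estimation: adjusted means by group over time, and between-group contrasts at each time point.

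**The concern.** A test of no difference answers whether the observed split of events would be surprising if the arms had equal risk. It does not say which excess risks remain plausible, and that is what the safety data of a pilot should tell whoever decides on a larger trial. If the number analysed is small, a non-significant result is compatible both with no excess and with a material one, and the p-value alone does not separate the two. As written, the plan produces no between-arm quantity for adverse events that does.

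**Working it through.** **Inputs.** The plan contains no power or sample-size figure for adverse events, so there is nothing to reproduce. From the document: two randomised arms, binary event endpoints, Fisher's exact or chi-squared test. Assumed, because not stated: 1:1 allocation; two-sided 5%; 15, 20, 30 or 50 analysed per arm; control versus patiromer event rates of 5% vs 20%, 5% vs 25% and 10% vs 30%.

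**Step 1: chance of missing a true excess.** For n per arm, take every pair (a, b) of event counts in the control and patiromer arms. The probability of a non-significant result is the sum of Bin(a; n, p1) × Bin(b; n, p2) over all pairs with p > 0.05. Chi-squared is uncorrected.

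| True rates | Test | n = 15 | n = 20 | n = 30 | n = 50 |
|---|---|---|---|---|---|
| 5% vs 20% | Fisher | 92% | 83% | 76% | 49% |
| | chi-squared | 81% | 71% | 55% | 34% |
| 5% vs 25% | Fisher | 83% | 70% | 56% | 25% |
| | chi-squared | 69% | 56% | 37% | 15% |
| 10% vs 30% | Fisher | 85% | 76% | 63% | 36% |
| | chi-squared | 72% | 64% | 50% | 27% |

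At 15 to 20 per arm every entry exceeds one half (56% to 92%). At 30 per arm this holds for Fisher (56% to 76%), but for chi-squared the entries run from 37% to 55%. At 50 per arm every entry is below one half. A very large excess is mostly detected even in small samples: 5% vs 50% is missed 26% (Fisher) or 13% (chi-squared) of the time at 15 per arm.

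**Step 2: what an interval adds.** Take assumed counts of 4/20 on patiromer and 1/20 on control.

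- Risk difference: 4/20 − 1/20 = 0.20 − 0.05 = +15 points.
- Fisher, two-sided: 2 × [C(20,0)·C(20,5) + C(20,1)·C(20,4)] / C(40,5) = 2 × (15,504 + 96,900) / 658,008 = 0.34.
- Chi-squared: 40 × (4·19 − 1·16)² / (20·20·5·35) = 144,000 / 70,000 = 2.06, p = 0.15.
- Miettinen-Nurminen 95% limits: the values d at which |0.15 − d| / √{[r1(1−r1)/20 + r2(1−r2)/20] × 40/39} = 1.96, where r1 and r2 are the maximum-likelihood rates subject to r1 − r2 = d. Result: −7 to +38 points. Newcombe's method gives −7 to +37.

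Both tests give a non-significant result, and the data are compatible with anything from a 7-point reduction to a 38-point excess.

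With 1/20 in each arm both p-values are 1.00, and the Miettinen-Nurminen interval is −20 to +20 points. Equal observed counts at that size still leave an excess of about 20 points open.

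**The case against.** The strongest reply is that the harm is hypothetical. The document states no safety hypothesis and no rule that a non-significant result means safe. It records events as rates and says they were reported, so with arm-level counts and denominators any reader could compute an interval. Adverse events are not the primary outcome. All of that stands. It limits the point to the p-value being the only stated inferential output. A reader might go further and infer that it would be the sole statistical basis for a safety statement, or that the investigators would read it as proof of safety. The document supports neither.

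A second reply is that the miss rates rest on assumed inputs, since the word pilot does not fix a sample size. This also stands. A reader might infer that large harm is usually missed whatever the size of the trial; the table above contradicts that at 50 per arm, for chi-squared in one of the three scenarios at 30, and for a 45-point excess at 15.

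A third reply is that a score interval may exclude zero where Fisher's test does not reject, so part of any contrast could reflect the choice of method. That is true of a table such as 6/20 versus 1/20 (Fisher p = 0.09, chi-squared p = 0.04, interval +1 to +48 points). It is why the example used here is one on which both tests and the interval agree that zero is not excluded.

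Finally, an interval will not settle safety at these sizes, and no margin of acceptable harm is proposed here. The interval's purpose is to show what is unresolved. None of these replies supplies the missing quantity: at any sample size, the stated test does not report how much excess harm the data allow.

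**Conclusion.** The point holds as a gap in the planned output. The only between-arm inference stated for adverse events is a test of no difference, without a risk difference or interval. That much follows from the document and needs no assumption. How often a material excess would go undetected is conditional: more often than not for excesses of 15 to 20 points at an assumed 15 to 20 analysed per arm with either test, and at 30 per arm with Fisher's test, given a two-sided 5% level and the control rates assumed above. It does not generally hold at 50 per arm or for very large excesses. The primary potassium analysis is unaffected. This is a cheap improvement that should be made, because it determines what the pilot can say about harm.

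**What to change.** Replace the adverse-event sentence in the Analysis paragraph with wording such as: *For hypoglycemia, hypomagnesemia and new gastrointestinal symptoms, the main safety result is the number and proportion of patients with the event in each arm and the risk difference (PAT minus SOC) with a two-sided 95% score confidence interval (Miettinen-Nurminen). P-values are supportive only. A non-significant p-value is not taken as evidence of no difference in safety.* Newcombe's interval would serve equally well; name one. State the number analysed per arm beside each result.

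The cost is one sentence and three interval calculations on data already recorded, so it can be done even if the tests have been run. The downside is that the intervals will be wide and will read less favourably than a statement of no significant difference. A score interval may also occasionally disagree with Fisher's test, which the report should acknowledge where it happens.
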